6.0 Registration Procedures

- 6.1 To register a patient, access the Lymphoma SPORE web page and enter the remote registration/randomization application. The registration/randomization application is available 24 hours a day, 7 days a week. Back up is available between 8 a.m. and 4:30 p.m. Central Time (Monday through Friday) by phone at [REDACTED]
[REDACTED]

The instructions for registration/randomization application are available on the Lymphoma SPORE secured web page and detail the process for completing and confirming patient registration. Prior to initiation of protocol treatment, this process must be completed in its entirety and a Lymphoma SPORE subject ID number must be available as noted in the instructions. It is the responsibility of the individual and institution registering the patient to confirm that the process has been successfully completed prior to release of the study agent. Patient registration via the registration/randomization application can be confirmed in any of the following ways:

- Contact the Lymphoma SPORE Registration Office [REDACTED] If the patient was fully registered, the Lymphoma SPORE Registration Office staff can access the information from the centralized database and confirm the registration.
- In the registration/randomization application, select the *Show Subject* button to verify that the patient registration data is retrievable.
- Enter the registration/randomization application and, using the Lymphoma SPORE subject ID, confirm the patient appears in the registration/randomization application.

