13.0 Treatment/Follow-up Decision at Evaluation of Patient

13.1 Patients will be evaluated per the test schedule during cycle 1 of treatment.

13.2 After treatment, patients will be observed at 3, 6, 9, 12, 18, 24, 30, 36, 48, and 60 months from day 1 of treatment.

13.3 Criteria for removing patients from treatment and initiating observation.

13.3.1 Requested withdrawal or patient non-compliance.

13.4 Patients who have progressive or relapsed disease, receive subsequent treatment for lymphoma, refuse further observation, or fail to return for evaluation during observation will go to event monitoring.

13.5 At 5 years from day 1 of treatment, all patients still on observation will go to event monitoring every 12 months until 10 years from time of registration per Section 18.0.

13.6 A patient is deemed *ineligible* if after registration, it is determined that at the time of registration, the patient did not satisfy each and every eligibility criteria for study entry.

The patient may continue protocol treatment at the discretion of the physician as long as there are no safety concerns, and the patient was properly registered. The patient will continue treatment (if no safety concerns), observation, and event monitoring as specified for all patients (or will be taken off study, if applicable).

- If the patient received treatment, the patient will continue treatment (if no safety concerns), observation, and event monitoring as specified for all patients.
- If the patient never received treatment, On-study material and the End of Active Treatment/Cancel Notification Form must be submitted. No further data submission is necessary.

13.7 A patient is deemed a *major violation*, if protocol requirements regarding treatment in cycle 1 of the initial therapy are severely violated that evaluability for primary end point is questionable. The patient may continue protocol treatment at the discretion of the physician as long as there are no safety concerns, and the patient was properly registered. The patient will continue treatment (if no safety concerns), observation, and event monitoring as specified for all patients.

13.8 A patient is deemed a *cancel* if he/she is removed from the study for any reason before any study treatment is given. On-study material and the End of Active Treatment/Cancel Notification Form must be submitted. No further data submission is necessary.

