16.0 Statistical Considerations and Methodology

16.1 Overview: This is a randomized phase III study designed to compare the complete response rate at 6 months between Rituximab (Arm A) and Zevalin (Arm B) for treatment of asymptomatic follicular lymphoma.

16.11 Primary Endpoint: The primary endpoint of this study is the complete response rate at the 6-month disease assessment which will be compared between the two arms. A patient is considered to be a complete responder if the objective status at the 6-month disease assessment is a complete response. Any patient not meeting the definition of a complete response will be considered as a non-responder for the primary endpoint. A modified intent-to-treat approach will be employed for the primary analysis such that all randomized subjects meeting the eligibility criteria who do not cancel participation prior to treatment initiation and did not experience a major treatment violation (during the first cycle of treatment) will be included in the primary analysis. Sensitivity analysis will be conducted including all patients who did not cancel participation prior to

treatment initiation. The percentage of patients in each response category (e.g., CR, PR, STAB, Relapse/PD) will also be tabulated by arm.

16.2 Statistical Considerations:

16.21 Statistical Design:

Previous studies of treatment with four doses of single agent Rituximab in this patient population have shown CR rates of 6-33% (9 and 10). In addition, preliminary results of an additional study, the RESORT ECOG trial, show a CR rate of 15% in this same population (11). This study is designed to detect an improvement in complete response rate from 20% with Rituximab (Arm A) to 50% with Zevalin (Arm B). The proportion of patients who have a CR at 6 months will be evaluated and compared between the two treatment regimens using a two-sided $\alpha=0.05$ continuity corrected Cochran–Mantel–Haenszel (CMH) test with stratification factors as defined in Section 5.0.

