The primary goal of this trial is to compare the CR rate at 6 months between Rituximab and Zevalin. We will randomize 116 evaluable patients in a 1:1 ratio to Rituximab or Zevalin. This final analysis will take place after all patients have completed the disease assessment at 6 months. A sample size of 58 evaluable patients per arm (116 total evaluable) provides 90% power to detect an improvement in complete response rate from 20% to 50%, using a two-sided chi-square test at a significance level of 0.05. To ensure that 116 evaluable patients are randomized, we will enroll/randomize **128 total patients**.

The CR rate in each arm will be estimated by the number of evaluable patients who achieve a CR as the objective status on the disease assessment at 6 months divided by the total number of randomized evaluable patients in that arm. The CR rates will be compared between the two arms. If the CR rate is higher in the Zevalin arm, where the p-value is less than 0.05, this will be considered sufficient evidence that the Zevalin arm may be recommended for further testing in subsequent studies.

This study will use a dynamic allocation procedure to allocate an equal number of patients to each of the two treatment regimens.(30) This procedure will balance the marginal distributions of the stratification factors between these two treatment arms. The stratification factors that will be used are listed in Section 5.0.

This study will be based on a modified intent-to-treat approach including all randomized patients meeting the eligibility criteria who do not cancel participation prior to treatment initiation and did not experience a major treatment violation (during the first cycle of treatment) based on the randomized treatment assignment.

The study will be permitted to be published after all patients have undergone the 6-month disease assessment to establish the CR rate between each arm. This essentially fulfills the first goal of the study. See Section 16.3 for further analysis plans.

16.23 Other considerations: Adverse events, quality/duration of response, and patterns of treatment failure observed in this study, as well as scientific discoveries or changes in standard care will be taken into account in any decision to terminate the study.

16.24 Sample Size: This study is expected to accrue a maximum of 128 patients unless undue toxicity is encountered.

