18.0 Records and Data Collection Procedures

18.1 Submission Timetable

Initial Material(s)

Case Report Form (CRF)	Active-Monitoring Phase (Compliance with Test Schedule Section 4.0)
On-Study	≤14 days after registration
Adverse Event– Baseline	
Measurement – Baseline	
Tumor Tissue Biopsy Pathology Report	
CT/PET/MRI Scan Report	
Research Paraffin Embedded Submission – Baseline (All Patients)	≤30 days after registration
Research Fresh Tissue Submission – Baseline (Mayo Patients only)	
Research Blood Submission	≤ 21 days after registration
End of Active Treatment/Cancel Notification	Submit ≤14 days after registration if withdrawal/refusal occurs prior to beginning protocol therapy
Patient Questionnaire Booklet	≤14 days after registration - Patient questionnaire booklet must be used; copies are not acceptable for this submission.
Booklet Compliance	≤14 days after registration - This form must be completed only if the patient questionnaire booklet contains absolutely NO patient provided assessment information.

Central Pathology Review Material(s)

CRF	Active-Monitoring Phase (Compliance with Test Schedule Section 4.0)
Pathology Materials (this is for central review, eligibility, etc.)	Submit ≤30 days after registration (see Section 17.0)

Test Schedule Material(s)

CRF	Active-Monitoring Phase (Compliance with Test Schedule Section 4.0)		
	At each evaluation during treatment	At end of treatment	Observation
Evaluation/Treatment	X ²	X	

CRF	Active-Monitoring Phase (Compliance with Test Schedule Section 4.0)		
	At each evaluation during treatment	At end of treatment	Observation
Evaluation/Observation			X ¹
Nadir/Adverse Event (Cycles 1 & 2 Only)	X	X	X ³
Measurement	X	X	X
Research Blood Submission			X (see Section 14.0)
Patient Questionnaire Booklet ⁴	X	X	X
Booklet Compliance ⁵	X	X	X
End of Active Treatment/Cancel Notification		X	
ADR/AER	At each occurrence (see Section 10.0)		At each occurrence (see Section 10.0) ³
CT/PET/MRI Scan Report	X ⁶		X ⁶

1. Complete at each evaluation during Observation (see Section 4.0).
2. Complete at each evaluation during Active Treatment (see Section 4.0).
3. AE form and expedited reports needed for Cycle 1 (treatment – months 0-3) and Cycle 2 (first cycle of observation – months 3-6) only.
4. Patient questionnaire booklet **must** be used; copies are not acceptable for this submission.

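### No planned CR analysis covers all randomised patients: those who cancel before treatment are left out of both the primary and the sensitivity analysis

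*Combined protocol and SAP*

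**What the plan says.** Section 16.11 defines a modified intent-to-treat (mITT) set for the primary analysis of CR at 6 months: "all randomized subjects meeting the eligibility criteria who do not cancel participation prior to treatment initiation and did not experience a major treatment violation" in cycle 1. Section 16.21 repeats it, "including all randomized patients meeting the eligibility criteria who do not cancel participation prior to treatment initiation", and takes the randomised evaluable patients in each arm as the CR denominator.

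Section 16.11 names one CR sensitivity analysis: "Sensitivity analysis will be conducted including all patients who did not cancel participation prior to" the start of treatment. The tabulation of response categories by arm states no population.

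Section 13.8 calls a patient a cancel "if he/she is removed from the study for any reason before any study treatment is given". The on-study material and a cancel form are then required, after which "No further data submission is necessary". Section 18.1 lists that form for use "if withdrawal/refusal occurs prior to beginning protocol therapy".

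Under the success rule in Section 16.21, if CR is higher on Zevalin with p below 0.05, "this will be considered sufficient evidence that the Zevalin arm may be recommended for further testing in subsequent studies".

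**The concern.** The sensitivity analysis relaxes two of the three mITT exclusions (ineligibility and major violation) and keeps the third. A patient who cancels before treatment is in no defined CR analysis set, although randomised and counted in the 128.

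That exclusion is the one most open to influence from the assigned arm. The protocol does not say that patients know their arm before cancelling, but it is a reasonable inference:

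- No blinding is described.
- Sites "enter the remote registration/randomization application" (6.1), so registration and randomisation share one step.
- Treatment may start up to 21 days later (6.6).
- Zevalin treatment is arranged after registration (7.3).
- Biosimilar insurance rules differ by arm (7.1, 7.2).

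Cancels could fall in either arm, since 19.1 describes both treatments as commercial standard of care. If cancelling depends on both arm and prognosis, the mITT comparison is biased, and the planned sensitivity analysis carries the same bias.

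**Working it through.** **The plan's own figure.** With CR of 20% v 50%, two-sided 0.05 and 90% power, the uncorrected formula is

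n' = [1.96·√(2·0.35·0.65) + 1.2816·√(0.2·0.8 + 0.5·0.5)]² / 0.30² = 51.01.

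The continuity correction gives n = (51.01/4)·[1 + √(1 + 4/(51.01·0.30))]² = 57.5, so 58 per arm. This matches Section 16.21, and the sample size is not in dispute. The allowance is 128 − 116 = 12 patients (9.4%).

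**Set-up.** The documents give no cancel rate or split by arm, so these are scenarios, not estimates. Assumptions: 64 randomised per arm; a single-stratum continuity-corrected Mantel–Haenszel test, whereas the planned test is stratified; exact binomial enumeration. The test is M² = (|a − E| − ½)²/V, where a is the number of CRs in Arm A, m the total CRs, E = n₁m/N and V = n₁n₂m(N − m)/[N²(N − 1)].

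**False results favouring Zevalin in the mITT set.** True CR is 20% among all randomised patients in both arms. If k patients in an arm cancel, each with CR chance f × 20%, the analysed rate in that arm is (64·0.20 − k·f·0.20)/(64 − k). Nominal one-sided error is 2.5%; with no cancels it is 1.5%.

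| Cancels A/B | f = 0 | f = 0.5 | f = 1 |
|---|---|---|---|
| 6/6 | 1.4% | 1.4% | 1.4% |
| 3/9 | 3.0% | 2.1% | 1.4% |
| 0/12 | 5.1% | 2.75% | 1.4% |
| 0/6 | 2.9% | 2.0% | 1.4% |
| 0/4 | 2.3% | 1.9% | 1.5% |

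The bias in the CR difference at 0/12 with f = 0 is 12.8/52 − 12.8/64 = 24.6% − 20.0% = 4.6 points. With f = 0.5 it is 11.6/52 − 20.0% = 2.3 points.

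**A result at the design effect.** 13/64 v 26/52 gives p = 0.002. Scoring 12 Arm B cancels as non-responders gives 13/64 v 26/64, p = 0.022.

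**A result near the boundary, 12 Arm B cancels.** For 13/64 v 22/52: N = 116, m = 35, E = 19.31, V = 6.10, M² = 5.81²/6.10 = 5.54, p = 0.019. With all 12 scored as non-CR (13/64 v 22/64): E = 17.5, V = 6.41, M² = 4.0²/6.41 = 2.50, p = 0.114.

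| CRs assumed among the 12 | 0 | 1 | 2 | 3 | 4 | 5 |
|---|---|---|---|---|---|---|
| p | 0.114 | 0.078 | 0.052 | 0.034 | 0.022 | 0.014 |

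The treated Arm B rate implies 12 × 22/52 = 5.1, about 5.

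**The mirror case, 12 Arm A cancels.** 10/52 v 22/64 gives p = 0.110. With 0, 1 or 2 CRs assumed among the 12, p is 0.025, 0.044 or 0.073. The treated Arm A rate implies 12 × 10/52 = 2.3, about 2.

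**Operating characteristics of non-responder scoring alone, cancels unrelated to response.**

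- At 20% v 50% with 12 Arm B cancels, the expected Arm B rate is 0.50 × 52/64 = 40.6%. Power falls to 66.4%, against 89.9% in the mITT set. With 6/6 it is 89.5%, against 90.0%.
- At equal CR with 12 Arm A cancels, the error favouring Zevalin rises to 4.9% (CR 20%) or 7.6% (CR 33%), against 1.25% and 1.5% in the mITT set.

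**The case against.** The strongest reply is that the headline scenarios stack assumptions. All 12 allowance patients must be cancels, although the 12 must also cover ineligible patients and major violations, whom the sensitivity analysis restores. They must fall in one arm and have little or no chance of CR. If cancelling were arm-neutral, 12 cancels would all fall in one arm with probability 2 × 0.5¹² = 0.05%, and split 9/3 or worse about 15% of the time. With four or fewer cancels, error stays below the nominal 2.5% even at f = 0. Eligibility criteria 3.19e (willing to travel) and 3.19i (insurance or willing to pay) remove some arm-related reasons. The form and the rule for cancels imply no expected number. Section 13.8 also covers removal for any reason, and excluding someone for a pre-randomisation fact need not bias anything.

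Most of this stands as a limit on size. Arm-neutral cancelling, however, is the assumption that needs checking, and no planned analysis checks it. The eligibility criteria are partial screens. Reporting reasons would separate removals on pre-randomisation facts from refusals of the assigned arm. The low-count results show when the gap is harmless; they do not supply the missing analysis. It is also fair that non-responder scoring alone can mislead, which argues for a two-direction analysis.

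**Conclusion.** The concern holds and should be fixed. Patients who cancel before treatment are outside every defined CR analysis set, so bias from arm-related cancelling would go undetected.

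Its size cannot be estimated from the documents. It is negligible if cancels are few, balanced or unrelated to response. At the assumed upper end (12 Arm B cancels, 20% true CR in both arms) it is 2.3 to 4.6 points on the CR difference and an error favouring Zevalin of 2.75% to 5.1%; Arm A cancels would push the other way. These figures rest on 64 per arm and an unstratified test. Only results nearer the boundary than the design effect depend on the cancels. The stakes are further bounded because success supports recommending further testing.

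**What to change.** Keep the mITT set as primary. In Sections 16.11 and 16.21, prespecify:

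1. A CR sensitivity analysis of all randomised patients by assigned arm, with cancels scored as non-responders. Section 16.11 already treats anyone without a CR as a non-responder.
2. A tipping-point version that varies the CR rate assumed for cancels separately in each arm. Report the Zevalin conclusion alongside it and, if the conclusion changes, state at which assumed rates.
3. A table of cancels by arm with reasons.

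The cost is wording. Arm is recorded at randomisation and the cancel form is already required, so no new data are needed. The drawback is that non-responder scoring works against whichever arm has more cancels, as the power and error figures above show. It should therefore be an added analysis read in both directions, not a replacement for the primary.

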5.0 Stratification Factors

- 5.1 Diagnosis: < 3 months vs. 3-12 months.
- 5.2 Beta-2 Microglobulin (using institutional values): normal vs. abnormal.
- 5.3 Lactate Dehydrogenase (using institutional values): normal vs. abnormal.

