- 11.111 Complete disappearance of all detectable clinical evidence of disease and definitely disease-related symptoms if present before therapy.
- 11.112 All lymph nodes and nodal masses must have regressed on CT to normal size (≤ 1.5 cm in their greatest transverse diameter for nodes > 1.5 cm before therapy). Previously involved nodes that were 1.1 to 1.5 cm in their long axis and more than 1.0 cm in their short axis before treatment must have decreased to ≤ 1.0 cm in their short axis after treatment. .
- 11.113 The spleen and/or liver, if considered enlarged before therapy on the basis of a physical examination or CT scan, should not be palpable on physical examination and should be considered normal size by imaging studies, and nodules related to lymphoma should disappear. However, determination of splenic involvement is not always reliable because a spleen considered normal in size may still contain lymphoma, whereas an enlarged spleen may reflect variations in anatomy, blood volume, the use of hematopoietic growth factors, or causes other than lymphoma. Similarly, other organs considered to be enlarged before therapy due to involvement by lymphoma, such as liver and kidneys, must have decreased in size.
- 11.114 If the bone marrow was involved by lymphoma before treatment, the infiltrate must have cleared on repeat bone marrow biopsy. The biopsy sample on which this determination is made must be adequate (with a goal of > 20 mm unilateral core). If the sample is indeterminate by morphology, it should be negative by immunohistochemistry. A sample that is negative by immunohistochemistry but that demonstrates a small population of clonal lymphocytes by flow cytometry will be considered a CR until data become available demonstrating a clear difference in patient outcome.

11.12 **Criteria for Partial Response (PR).** The designation of PR requires all of the following:

- 11.121 At least a 50% decrease in sum of the product of the diameters (SPD) of up to six of the largest dominant nodes or nodal masses. These nodes or masses should be selected according to all of the following:
 - they should be clearly measurable in at least 2 perpendicular dimensions
 - if possible they should be from disparate regions of the body
 - they should include mediastinal and retroperitoneal areas of disease whenever these sites are involved
- 11.122 No increase should be observed in the size of other nodes, liver, or spleen.

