- 11.123 Splenic and hepatic nodules must regress by $\geq 50\%$ in their SPD or, for single nodules, in the greatest transverse diameter.
- 11.124 With the exception of splenic and hepatic nodules, involvement of other organs is usually assessable and no measurable disease should be present.
- 11.125 Bone marrow assessment is irrelevant for determination of a PR if the sample was positive before treatment. However, if positive, the cell type should be specified (eg, large-cell lymphoma or small neoplastic B cells). Patients who achieve a CR by the above criteria, but who have persistent morphologic bone marrow involvement will be considered partial responders.
When the bone marrow was involved before therapy and a clinical CR was achieved, but with no bone marrow assessment after treatment, patients should be considered partial responders.
- 11.126 No new sites of disease should be observed.
- 11.127 CT criteria should be used

11.13 **Criteria for Stable Disease (SD)**

- 11.131 A patient is considered to have SD when he or she fails to attain the criteria needed for a CR or PR (see above), but does not fulfill those for progressive disease (see below).
- 11.132 There must be no change in the size of the previous lesions on the post-treatment CT scan.

11.14 **Relapsed Disease (after CR)/Progressive Disease (PD) (after PR, SD):**
Lymph nodes should be considered abnormal if the long axis is more than 1.5 cm regardless of the short axis. If a lymph node has a long axis of 1.1 to 1.5 cm, it should only be considered abnormal if its short axis is more than 1.0. Lymph nodes $\leq 1.0 \times \leq 1.0$ cm will not be considered as abnormal for relapse or progressive disease.

- 11.141 Appearance of any new lesion more than 1.5 cm in any axis during or at the end of therapy, even if other lesions are decreasing in size. Increased FDG uptake in a previously unaffected site should only be considered relapsed or progressive disease after confirmation with other modalities. In patients with no prior history of pulmonary lymphoma, new lung nodules identified by CT are mostly benign. Thus, a therapeutic decision should not be made solely on the basis of the PET without histologic confirmation.

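### Baseline marrow involvement is part of the 6-month CR definition but is neither balanced nor adjusted for; the planned test stays valid, and a prespecified adjusted risk difference would protect the estimate against chance imbalance

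*Combined protocol and SAP*

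**What the plan says.** - **Primary test (16.21).** A two-sided, continuity-corrected CMH "test with stratification factors as defined in Section 5.0". The three factors in Section 5.0 are time since diagnosis ("Diagnosis: < 3 months vs. 3-12 months"), beta-2 microglobulin and LDH.
- **Allocation (16.21).** Dynamic allocation balances those three factors only. The CR rate reported for each arm is a raw proportion.
- **CR definition (11.114).** "If the bone marrow was involved by lymphoma before treatment, the infiltrate must have cleared on repeat bone marrow biopsy".
- **Missing repeat marrow (11.125).** For a clinical CR with marrow involved before therapy, "but with no bone marrow assessment after treatment, patients should be considered partial responders". Persistent marrow disease has the same result. Under 16.11 anything short of CR is a non-response.
- **Availability.** Marrow examination is an eligibility requirement (3.19h). Marrow involvement is coded yes/no for FLIPI2 in Section 12.1, as a descriptive factor only. Section 4.0, footnote 6, limits the repeat biopsy to patients positive at baseline.
- **Sensitivity analysis (16.11).** The only one planned changes the population, not the covariates.
- **Sample size (16.21).** "A sample size of 58 evaluable patients per arm (116 total evaluable) provides 90% power" for 20% versus 50%, "using a two-sided chi-square test at a significance level of 0.05".

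**The concern.** Most omitted baseline covariates are only possibly prognostic. Here the link to the outcome is written into the endpoint. With the same CT and examination findings, a marrow-positive patient can do no better than a marrow-negative one, and a missed or positive month-6 biopsy turns a clinical CR into a non-response. Beta-2 microglobulin and LDH are adjusted for, although neither enters the CR definition.

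With 58 patients per arm the marrow-positive share can differ noticeably by chance, and the raw CR difference carries that imbalance. At stake is how well the one realised estimate reflects the treatment effect, and how it can be defended if the baseline table shows an imbalance. A marrow adjustment added after that table is seen would look data-driven.

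**Working it through.** **1. The plan's own figure.** Inputs from 16.21: CR 20% and 50%, two-sided alpha 0.05, 90% power, 1:1 allocation.

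- Uncorrected: n = [1.960·√(2·0.35·0.65) + 1.282·√(0.2·0.8 + 0.5·0.5)]² / 0.30² = 51.0, so 52 per arm.
- Continuity-corrected: (51.0/4)·[1 + √(1 + 4/(51.0·0.30))]² = 57.5, so **58 per arm**, as stated.
- Corrected power at 58 per arm is 90.3% by formula and 90.6% by exact enumeration.

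Omitting marrow does not make the sample size wrong.

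**2. Assumptions, because the documents give neither figure.** Marrow-positive share m of 30–50%; CR gap g of 15–30 points between marrow-negative and marrow-positive patients, equal in both arms; overall CR 20% and 50%. Arm A CR in marrow-positive patients is 0.20 − g(1 − m). At m = 30% and g = 30 points this is 0.20 − 0.21 = −1%, which is impossible, so that combination is excluded. At m = 40% and g = 30 points it is 2%, so the upper end of the gap is extreme.

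**3. Size of chance imbalance.** SD = √(2m(1 − m)/58), with simple equal allocation assumed. More than 12 points means at least 7 patients (7/58 = 12.1%). The last two columns come from enumerating two binomials of size 58.

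| m | SD (points) | P(Arm B > 12 points higher) | Mean imbalance in those trials (points) |
|---|---|---|---|
| 30% | 8.5 | 9.4% | 15.2 |
| 40% | 9.1 | 10.9% | 15.6 |
| 50% | 9.3 | 11.4% | 15.7 |

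**4. Effect on the raw difference.** Expected raw difference = 30 − g × imbalance.

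- m = 30%, g = 15: 30 − 0.15·15.2 = 27.7 points.
- m = 30%, g = 25: 30 − 0.25·15.2 = 26.2 points.
- m = 40%, g = 30: 30 − 0.30·15.6 = 25.3 points.
- m = 50%, g = 30: 30 − 0.30·15.7 = 25.3 points.

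An equal imbalance the other way adds the same amount, so the average over all trials stays at 30.

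**5. Power given the imbalance.** Simulated planned CMH (4,000 trials per scenario, m = 40%, Section 5.0 factors assumed non-prognostic with prevalences 50%, 25% and 15%):

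| True CR | Gap | Arm B ≥ 10 points more marrow-positive | Arm B ≥ 10 points fewer |
|---|---|---|---|
| 20% vs 50% | 15 | 80% | 93% |
| 20% vs 50% | 30 | 76% | 96% |
| 20% vs 40% (3,000 trials) | 30 | 35% | 75% |

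With marrow as an added stratum, the second row becomes about 88% both ways and the third about 56% both ways.

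**6. Type I error.** With CR 30% in both arms, the planned CMH rejects in 2.7–3.2% of trials, and in no more than 4.9% within either imbalanced subset. There is no inflation.

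**7. Average gain from adjustment.** Linear risk difference with robust standard errors, three factors without and then with marrow, 20,000 trials per scenario. Power rises by 0.3 points (m = 30% or 40%, g = 15), 0.8 (m = 40%, g = 20), 1.4 (m = 30%, g = 25) and 2.2 (m = 40%, g = 30), and by 2.5 at the most favourable corner (m = 50%, g = 30). With g = 0 it falls by about 0.4. Type I error of the adjusted analysis is about 5%.

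**8. Marrow as a fourth crossed stratum.** With g = 0, the continuity-corrected CMH falls from 88.4% power (8 strata) to 86.4% (16 strata).

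**The case against.** The strongest reply is that nothing in the plan is wrong. The test matches the allocation factors, its error rate already covers chance imbalance in unstratified covariates, and adding one more covariate is a design preference. That stands as far as validity goes. A reader might infer that the primary comparison is biased, that its type I error is inflated or that the trial is undersized. Steps 1, 4 and 6 do not support any of these.

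Second, the definitional link proves the direction of the gap, not its size. By definition alone, the gap is the probability of being CT-clear multiplied by the probability that the marrow has not cleared or was not examined. Eligibility caps involvement below 25%, and the documents do not say how often such marrow fails to clear. If that is rare, there is little to adjust for. This stands, and every magnitude here depends on it. If beta-2 microglobulin or LDH correlates with marrow status, part of the effect is already recovered.

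Third, the decision seldom changes. Comparing unstratified and marrow-stratified CMH tests at 20% versus 50%, the significance verdict differed in about 2–3% of trials at gaps of 15–20 points and about 5% at 30 points. This also stands, and it is why replacing the formal test is not warranted.

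Fourth, the covariate is not perfectly uniform. Criterion 3.19h asks for bilateral sampling, while Section 4.0 allows unilateral or bilateral sampling and accepts a marrow up to 180 days old. A yes/no variable tolerates this, but it should be defined in advance.

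**Conclusion.** The concern holds as one of precision and conditional imbalance. A variable that enters the primary endpoint's definition, and is known for every patient before randomisation, is left out of both the allocation and the CR analysis. Under the assumed shares and gaps, about 9–11% of trials have Arm B more than 12 points more marrow-positive, and the raw difference is then about 2 to 5 points too low; the mirror-image imbalance overstates it by as much. This is moderate against the 30-point design difference and matters more if the true effect is smaller. The average power gain is small and is not the reason to act. The reason is that the imbalance is foreseeable from the endpoint definition and inexpensive to guard against beforehand. The sizes rest on assumed inputs, a gap equal in both arms, simple rather than dynamic allocation, and non-prognostic Section 5.0 factors.

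**What to change.** Before the primary analysis, add to 16.21 a main-effects covariate-adjusted risk difference for 6-month CR (standardised logistic, or linear with robust standard errors). Include the three Section 5.0 factors plus baseline marrow involvement (yes/no, as coded for FLIPI2), and report it with its confidence interval beside the stratified CMH result. The CMH may remain the formal test. Do not add marrow as a fourth crossed stratum: 16 strata for 116 patients cost about 2 points of power if marrow is not prognostic. State the rule for deriving marrow status, given the unilateral/bilateral wording.

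The cost is SAP wording only, with no new data and no more patients. The downside is a model-based estimate. Adjustment does not repair missed month-6 biopsies, which remain non-responses; tabulating them by arm would show whether they differ.
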